4.2.3.6 Future Biomedical Research

The Sponsor will conduct Future Biomedical Research on specimens collected for future biomedical research during this clinical trial. This research may include genetic analyses (DNA), gene expression profiling (RNA), proteomics, metabolomics (serum, plasma) and/or the measurement of other analytes.

Such research is for biomarker testing to address emergent questions not described elsewhere in the protocol (as part of the main trial) and will only be conducted on specimens from appropriately consented subjects. The objective of collecting specimens for Future Biomedical Research is to explore and identify biomarkers that inform the scientific understanding of diseases and/or their therapeutic treatments. For instance, exploratory pharmacogenetic (PGt) studies may be performed if significant Pharmacokinetic/Pharmacodynamic (PK/PD) relationships are observed or adverse events are identified. Genomic markers of disease may also be investigated. Such retrospective pharmacogenetic studies will be conducted with appropriate biostatistical design and analysis and compared to PK/PD results or clinical outcomes. Any significant PGt relationships to outcome would require validation in future clinical trials. The overarching goal is to use such information to develop safer, more effective drugs/vaccines, and/or to ensure that subjects receive the correct dose of the correct drug/vaccine at the correct time. The details of this Future Biomedical Research sub-trial are presented in Section 12.2 - Collection and Management of Specimens for Future Biomedical Research. Additional informational material for institutional review boards/ethics committees (IRBs/ERCs) and investigational site staff is provided in Section 12.3.

4.3 Benefit/Risk

Subjects in clinical trials generally cannot expect to receive direct benefit from treatment/vaccination during participation, as clinical trials are designed to provide information about the safety and effectiveness of an investigational medicine.

Additional details regarding specific benefits and risks for subjects participating in this clinical trial may be found in the accompanying Investigators Brochure (IB) and Informed Consent documents.

5.0 METHODOLOGY

5.1 Entry Criteria

5.1.1 Diagnosis/Condition for Entry into the Trial

Female and male subjects of at least 18 years of age with metastatic triple-negative breast cancer (mTNBC) will be enrolled in this trial.

5.1.2 Subject Inclusion Criteria

In order to be eligible for participation in this trial, the subject must:

For Cohorts A and C (2L+ monotherapy), potential subjects must:

1. Have received at least one systemic treatment for metastatic breast cancer and have documented disease progression on or after the most recent therapy. Subjects must have been previously treated with an anthracycline and a taxane in the (neo)adjuvant or metastatic setting.

Note for Cohort A: In the event that the interim analysis shows that pembrolizumab monotherapy is futile in subjects with PD-L1 (-) mTNBC, subsequent enrollment to Cohort A may be limited to subjects with PD-L1 (+) tumors. If this is the case, sites will be notified via a Protocol Clarification Letter.

For the purposes of this study, neoadjuvant and/or adjuvant chemotherapy regimens do not count as a prior line of therapy.

For Cohort B (1L monotherapy), potential subjects must:

2. Have not received prior systemic anti-cancer therapy for mTNBC, **and**
3. Have PD-L1 (+) mTNBC.

For the purposes of this study, neoadjuvant and/or adjuvant chemotherapy regimens do not count as a prior line of therapy.

For Cohort C (2L+ monotherapy), potential subjects must:

4. Have PD-L1 strong (+) mTNBC, i.e. subject's tumor must meet or exceed the PD-L1 cut point for high positivity.

For all cohorts, potential subjects must:

5. Be willing and able to provide written informed consent/assent for the trial. The subject may also provide consent/assent for Future Biomedical Research. However, the subject may participate in the main trial without participating in Future Biomedical Research.
6. Be \geq 18 years of age on day of signing informed consent.
7. Be a female or male subject with mTNBC. Central determination of triple-negative breast cancer status is required for enrollment.

8. Have provided tumor tissue for PD-L1 biomarker analysis from a newly obtained core or excisional biopsy of a not-previously-irradiated metastatic tumor lesion (mandatory). Adequacy of the biopsy specimen for PD-L1 biomarker analysis must be confirmed by the central analysis laboratory. Repeat samples may be required if adequate tissue is not provided.
 - a. Note: Subjects for whom tumor biopsies cannot be newly obtained (e.g. inaccessible tumor or subject safety concern) may submit an archived metastatic tumor specimen only upon agreement from the Sponsor.
 - b. Note: If emerging data demonstrates that there is no difference in the clinical utility of PD-L1 assessment in newly obtained samples relative to archived ones, then archived samples may be acceptable without Sponsor agreement. If this is the case, sites will be notified via an Administrative Memo.
 - c. Note: For subjects with mTNBC at the time of initial breast cancer diagnosis, who did not have breast surgery and/or breast radiation therapy, a newly obtained core or excisional biopsy from the existing breast tumor mass may be obtained for eligibility determination.
9. Have measurable metastatic disease based on RECIST 1.1 as determined by the central imaging vendor. Tumor lesions situated in a previously irradiated area are considered measurable, if radiographic progression has been demonstrated in such lesions.
 - a. Note: The same imaging modality, acquisition and technical parameters should be used throughout the study for tumor imaging.
10. Have a performance status of 0 or 1 on the ECOG Performance Scale. Assessment should be performed within 10 days of treatment initiation.
11. Female subjects of childbearing potential should be willing to use 2 methods of birth control or be surgically sterile, or abstain from heterosexual activity for the course of the study through 120 days after the last dose of study medication (Reference Section 5.7.2). Subjects of childbearing potential are those who have not been surgically sterilized or have not been free from menses for > 1 year.

Male subjects should agree to use an adequate method of contraception starting with the first dose of study therapy through 120 days after the last dose of study therapy.

Abstinence is acceptable if this is the usual lifestyle and preferred contraception for the subject.
12. Demonstrate adequate organ function as defined in [Table 2](#). All screening labs should be performed within 10 days of treatment initiation.

Table 2 Adequate Organ Function Laboratory Values

System	Laboratory Value
Hematological	
Absolute neutrophil count (ANC)	≥1,500 /mCL
Platelets	≥100,000 / mCL
Hemoglobin	≥9 g/dL or ≥5.6 mmol/L without transfusion or EPO dependency
Renal	
Creatinine OR Measured or calculated ^a creatinine clearance (CrCl)	≤1.5 X upper limit of normal (ULN) OR ≥30 mL/min for subject with creatinine levels > 1.5 X institutional ULN
[Glomerular filtration rate (GFR) can also be used in place of creatinine or CrCl]	
Hepatic	
Total bilirubin	≤ 1.5 X ULN OR Direct bilirubin ≤ULN for subjects with total bilirubin levels >1.5xULN
Aspartate aminotransferase [AST (SGOT)] and alanine aminotransferase [ALT (SGPT)]	≤ 2.5 X ULN
Albumin	≥3.0 g/dL
Lactate Dehydrogenase (LDH)	< 2.5 X ULN
Coagulation	
International Normalized Ratio (INR) or Prothrombin Time (PT)	≤1.5 X ULN unless subject is receiving anticoagulant therapy as long as PT or PTT is within therapeutic range of intended use of anticoagulants
Activated Partial Thromboplastin Time (aPTT)	≤1.5 X ULN unless subject is receiving anticoagulant therapy as long as PT or PTT is within therapeutic range of intended use of anticoagulants
^a Creatinine clearance should be calculated per institutional standard.	

13. Female subjects of childbearing potential should have a negative urine or serum pregnancy test within 72 hours prior to receiving the first dose of study medication. If the urine test is positive or cannot be confirmed as negative, a serum pregnancy test will be required.

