5.7.2 Contraception

Pembrolizumab may have adverse effects on a fetus in utero. Furthermore, it is not known if pembrolizumab has transient adverse effects on the composition of sperm. Non-pregnant, non-breast-feeding women may be enrolled if they are willing to use 2 methods of birth control or are considered highly unlikely to conceive. Highly unlikely to conceive is defined as 1) surgically sterilized, or 2) postmenopausal (a woman who is ≥ 45 years of age and has not had menses for greater than 1 year will be considered postmenopausal), or 3) not heterosexually active for the duration of the study. The two birth control methods can either be two barrier methods or a barrier method plus a hormonal method to prevent pregnancy. Subjects should start using birth control from study Visit 1 throughout the study period up to 120 days after the last dose of study therapy.

The following are considered adequate barrier methods of contraception: diaphragm, condom (by the partner), copper intrauterine device, sponge, or spermicide as per local regulations or guidelines. Appropriate hormonal contraceptives will include any registered and marketed contraceptive agent that contains an estrogen and/or a progestational agent (including oral, subcutaneous, intrauterine, or intramuscular agents).

Note: Abstinence is acceptable if this is the usual lifestyle and preferred contraception for the subject.

Subjects should be informed that taking the study medication may involve unknown risks to the fetus (unborn baby) if pregnancy were to occur during the study. In order to participate in the study they must adhere to the contraception requirement (described above) for the duration of the study and during the follow-up period defined in section 7.2.2-Reporting of Pregnancy and Lactation to the Sponsor. If there is any question that a subject will not reliably comply with the requirements for contraception, that subject should not be entered into the study.

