- l. For women of reproductive potential, a urine or serum pregnancy test should be performed within 72 hours prior to first dose of trial treatment. If the urine test is positive or cannot be confirmed as negative, a serum pregnancy test will be required. Pregnancy tests (serum and/or urine tests) should be repeated if required by local guidelines.
- m. Blood for menopausal status may be required for certain subjects as described in Section 7.1.3.2.
- n. Coagulation factors (PT/INR and aPTT) should be tested as part of the screening procedures for all subjects.
- o. Laboratory tests for screening are to be performed within 10 days prior to the first dose of trial treatment. See Section 7.1.3 for details regarding laboratory tests.
- p. After Cycle 1, lab samples can be collected up to 72 hours prior to the scheduled time point. See Section 7.1.3 for details regarding laboratory tests.
- q. Blood draws for thyroid function tests should be done prior to dosing at the scheduled timepoint, however results can be reviewed after dosing. These tests are to be repeated every 2 cycles after Cycle 6.
- r. Unresolved abnormal labs that are drug related AEs should be followed until resolution. Labs do not need to be repeated after the end of treatment if labs are within normal range.
- s. Both PK and anti-pembrolizumab antibody for subjects who receive pembrolizumab; Pre-dose trough PK and anti-pembrolizumab antibody samples will be collected at Cycles 1, 2, 4, 6, 8 and every 4 cycles thereafter, 30 days after discontinuation of study drug, and 3 months after discontinuation of study drug (or until the subject starts new anti-cancer therapy). All pre-dose trough PK samples should be drawn within 24 hours before infusion of pembrolizumab.
- t. PK for pembrolizumab sample collection only: Additional post-dose peak PK samples will be drawn within 30 minutes after end of pembrolizumab infusion at Cycles 1 and 8. An additional single PK sample should be drawn at 24 hours (Day 2), between 72 and 168 hours (Day 4-8) and 336 hours (Day 15) after Cycle 1 dosing.

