7.1.3.2 Blood for Menopausal Status

Blood for evaluation of postmenopausal status (FSH and estradiol) will be evaluated if clear documentation of post-menopausal status is not obtained.

The menopausal status (pre- or post-menopausal) for all subjects younger than age 60 must be determined at screening according to the definitions below. The date of the subject's last menstrual period (LMP), bilateral ovariectomy/oophorectomy status (if applicable) and, when indicated, serum FSH and estradiol levels, must be assessed and recorded in the eCRFs.

Pre-menopausal

- ≤ 12 months since LMP
- OR**
- Biochemical evidence of pre-menopausal status according to serum FSH and estradiol levels and local institutional guidelines

Post-menopausal

- Subject has undergone prior bilateral ovariectomy/oophorectomy
- OR**
- >12 months since LMP **and** no hysterectomy, hormone replacement, estrogen receptor antagonist, chemotherapy or ovarian suppression at any time since LMP
- OR**
- Biochemical evidence of post-menopausal status according to serum FSH and estradiol levels and local institutional guidelines.

Blood collection at screening for biochemical evidence of menopausal status (FSH and estradiol) will be needed if patient:

1. Is ≤ 60 years old, and
2. has not had a bilateral oophorectomy, and
3. has not had a menstrual period for at least 12 months, and
4. had a hysterectomy or was on hormone replacement, estrogen receptor antagonist, chemotherapy or ovarian suppression at any time since LMP.

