7.1.5.2.1 Second Course Phase (Retreatment Period)

Subjects who stop pembrolizumab with SD or better may be eligible for up to an additional 17 cycles (approximately one year) of pembrolizumab therapy if they progress after stopping study treatment. This retreatment is termed the Second Course Phase of this study and is only available if the study remains open and the subject meets the following conditions:

- **Either**
 - Stopped initial treatment with pembrolizumab after attaining an investigator-determined confirmed CR according to RECIST 1.1, and
 - Was treated for at least 8 cycles (24 weeks) with pembrolizumab before discontinuing therapy
 - Received at least two treatments with pembrolizumab beyond the date when the initial CR was declared

OR

- Had SD, PR or CR and stopped pembrolizumab treatment after 35 administrations (approximately 24 months) of study therapy for reasons other than disease progression or intolerability

AND

- Experienced an investigator-determined confirmed radiographic disease progression after stopping their initial treatment with pembrolizumab
- Did not receive any anti-cancer treatment since the last dose of pembrolizumab

- Has a performance status of 0 or 1 on the ECOG Performance Scale
- Demonstrates adequate organ function as detailed in Section 5.1.2
- Female subject of childbearing potential should have a negative serum or urine pregnancy test within 72 hours prior to receiving retreatment with study medication.
- Female subject of childbearing potential should be willing to use 2 methods of birth control or be surgically sterile, or abstain from heterosexual activity for the course of the study through 120 days after the last dose of study medication (Reference Section 5.7.2). Subjects of child bearing potential are those who have not been surgically sterilized or have been free from menses for > 1 year.
- Does not have a history or current evidence of any condition, therapy, or laboratory abnormality that might interfere with the subject's participation for the full duration of the trial or is not in the best interest of the subject to participate, in the opinion of the treating investigator.
- The subject meets the safety parameters listed in the inclusion/exclusion criteria.
- The trial is ongoing.

Subjects who restart treatment will be retreated at the same dose and dose interval as when they last received pembrolizumab. Treatment will be administered for up to one additional year.

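### Entry and retreatment criteria define childbearing potential in contradictory terms, and the entry definition lacks the age condition of the contraception section it cites

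*Combined protocol and SAP*

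**What the plan says.** The term childbearing potential is defined twice in the protocol.

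- Section 5.1.2, criterion 11 (entry): "Subjects of childbearing potential are those who have not been surgically sterilized or have not been free from menses for > 1 year".
- Section 7.1.5.2.1 (Second Course Phase): "Subjects of child bearing potential are those who have not been surgically sterilized or have been free from menses for > 1 year".

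Both refer the reader to Section 5.7.2 for contraception. That section uses a different concept, women highly unlikely to conceive. It exempts those who are surgically sterilised, postmenopausal or not heterosexually active. For the second group it says "a woman who is ≥ 45 years of age and has not had menses for greater than 1 year will be considered postmenopausal".

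The pre-dose pregnancy test depends on the defined term. Criterion 13 reads "Female subjects of childbearing potential should have a negative urine or serum pregnancy test within 72 hours", and the retreatment list has the parallel "Female subject of childbearing potential should have a negative serum or urine pregnancy test within 72 hours". Footnote a of Table 7 (Section 7.1.3.1) restricts the test to women of childbearing potential. The flow chart uses another label: "For women of reproductive potential, a urine or serum pregnancy test should be performed within 72 hours prior to first dose of trial treatment" (Section 6.1, footnote l). Footnote k of Section 6.2 and the screening text in Section 7.1.5.1 use the same label, reproductive potential. It is not defined anywhere.

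**The concern.** These definitions decide who is tested before the first dose and who must use two contraceptive methods. Section 5.7.2 warns of possible harm to a fetus. In the initial treatment phase the flow chart schedules one pregnancy test, at screening, and leaves repeats to local guidelines, so a woman who falls outside the definition at entry may not be tested at all.

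A site that looks up the rule finds two definitions that differ by one negation, a third passage with an age threshold the first lacks, and a separate label in the visit schedule. Two sites could handle the same woman differently, each with the protocol on its side.

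**Working it through.** No plan figure is involved, so the check sets the passages side by side. Write S for surgically sterilised and A for free from menses for more than 1 year. The word 'or' in the two definitions can be read in two ways.

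- *Literal* (either condition suffices). Criterion 11: not S, or not A. Section 7.1.5.2.1: not S, or A.
- *Ordinary* (a woman leaves the group if sterilised or amenorrhoeic). Criterion 11: not S and not A. The same construction applied to the printed words of 7.1.5.2.1 gives: not S and A.
- Section 5.7.2, abstinence set aside: contraception is needed unless S, or (age ≥ 45 and A).

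Six profiles, with yes meaning of childbearing potential (for 5.7.2, contraception needed):

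| Profile | Crit. 11 literal | Crit. 11 ordinary | 5.7.2 | 7.1.5.2.1 literal | 7.1.5.2.1 ordinary |
|---|---|---|---|---|---|
| 1. Age 35, not S, A | yes | no | yes | yes | yes |
| 2. Age 48, not S, A | yes | no | no | yes | yes |
| 3. Age 35, not S, menstruating | yes | yes | yes | yes | no |
| 4. Age 55, not S, natural menopause | yes | no | no | yes | yes |
| 5. Age 40, S, A | no | no | no | yes | no |
| 6. Age 35, S (tubal ligation), menstruating | yes | no | no | no | no |

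*Criterion 11 against 5.7.2.* On the literal reading they disagree for profiles 2, 4 and 6. Every unsterilised postmenopausal woman is of childbearing potential under criterion 11, while 5.7.2 exempts her. On the ordinary reading they disagree for profile 1 only. She needs contraception under 5.7.2, but criterion 13 and Table 7 do not call for her test.

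*Criterion 11 against 7.1.5.2.1.* On the literal reading they disagree for profiles 5 and 6. Sterilisation already satisfies the contraception clause in both places, so only the test is at issue there. On the ordinary reading they disagree for profiles 1 to 4. That includes profile 3, a menstruating, unsterilised woman whom the retreatment wording would leave out. The reversed clause is therefore not simply over-inclusive.

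*If the reversal is treated as a lost 'not' and silently corrected,* entry and retreatment agree. The disagreement with 5.7.2 remains: profile 1 on the ordinary reading, or profiles 2, 4 and 6 on the literal one. Correcting that one word is not enough.

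**The case against.** The strongest reply is that the reading standard must not be switched between sections. Read literally throughout, the 35-year-old in profile 1 is of childbearing potential at entry and at retreatment and needs contraception under 5.7.2. Read by evident intent throughout, the retreatment sentence is criterion 11 with a word missing. This stands as far as it goes: her missing test at entry depends on the ordinary reading of criterion 11. It does not reconcile the text, because each consistent reading still leaves a conflict with 5.7.2.

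A reader might infer that such a woman would be let in without contraception. The documents do not support that. Section 5.7.2 is itself a condition of enrolment and is cited by criterion 11, so its age condition applies to her. What is in doubt at entry on the ordinary reading is the test, not contraception.

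A reader might also take Section 7.1.3.2 as a further conflicting definition, because it asks for FSH and estradiol when an amenorrhoeic woman "had a hysterectomy or was on hormone replacement, estrogen receptor antagonist, chemotherapy or ovarian suppression at any time since LMP". That section classifies menopausal status, which Section 8.2.8 uses as a subgroup variable. It says nothing about pregnancy testing or contraception, and a stricter rule for another purpose is not a contradiction.

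There are also safeguards. Exclusion criterion 12 bars pregnant women however the term is defined, and the flow-chart label may bring profile 1 in for testing. But the exclusion does not say who is tested, and the label is undefined. At retreatment the same list also requires the safety parameters of the entry criteria to be met, which may bring the entry wording back in alongside the reversed one without saying which prevails.

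**Conclusion.** The contradiction is in the text and needs no assumption: the two definitions differ in the sign of the menses clause, and criterion 11 omits the age condition of the section it cites. Which women are affected depends on how 'or' is read, as the table shows.

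The size cannot be put as a headcount. The documents do not give the number of women under 45 with more than a year of amenorrhoea. The association of TNBC with younger age and premenopausal status (Section 4.2.1) and the required anthracycline and taxane exposure in Cohorts A and C make profile 1 plausible, but do not show how common she is. The reversed clause matters only in the Second Course Phase.

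Nothing in the ORR estimation, the interim analyses or the sample size changes. This is an inconsistency in operative eligibility and safety wording. It should be corrected because it governs a pregnancy test and contraception, but it does not threaten the trial's conclusions.

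**What to change.** Reconcile criterion 11, Section 5.7.2 and Section 7.1.5.2.1 into one definition. State it once, and cite it without restating it in criteria 11 and 13, footnote a of Table 7, footnote l of Section 6.1, footnote k of Section 6.2, Section 7.1.5.1 and Section 7.1.5.2.1. Use one term throughout in place of the two now in use.

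The definition has to settle three things:

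1. whether being free from menses for more than a year puts a woman in the group or takes her out of it;
2. whether the two conditions are joined by 'and' or by 'or';
3. whether an age condition applies, and if so, to testing as well as contraception.

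The sponsor's clinical team should choose the rule; this review does not propose one. The team may also state whether the FSH and estradiol result already collected from some women under Section 7.1.3.2 bears on the classification.

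The cost is wording in an amendment and, depending on the rule chosen, at most a few additional pregnancy tests of a type the protocol already uses.
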